9.2. Statistical Methods and Properties

9.2.1. Statistical Methods for Dose Escalation/De-Escalation

Many alternative designs have been proposed to the standard 3+3 design for Phase 1 dose escalation studies that improve its accuracy, efficiency and statistical validity.

The traditional mTPI design (Ji et al., 2010)²⁹ uses a Bayesian statistics framework and a beta/binomial hierarchical model to compute the posterior probability of 3 dosing intervals that reflect the relative difference between the toxicity rate of each dose level to the target rate ($p_T = 0.275$). If the toxicity rate of the currently used dose level is far smaller than p_T , the mTPI will recommend escalating the dose level; if it is close to target probability (p_T), the mTPI will recommend continuing at the current dose; if it is far greater than p_T , the mTPI will recommend de-escalating the dose level. These rules are conceptually similar to those used by the 3+3 design, except the decisions of an mTPI design are based on posterior probabilities calculated under a coherent probability model. The proposed modified TPI method for this protocol includes stopping rules and dose escalation/finding criteria, which prevents the target DLT rate to reach $\geq 33\%$ for determining the MTD. This proposed mTPI method is more conservative than the traditional TPI method. Being a rule-based design, mTPI automatically and appropriately tailors dose-escalation and de-escalation decisions for different studies with different toxicity parameters. More importantly, all the dose-escalation and de-escalation decisions for a given study can be pre-calculated under the mTPI design and presented in a two-way table (See [Section 3.1.5](#)). Thus, compared to other advanced model-based designs published in the literature, the mTPI design is logistically less complicated and easier to implement. Recently, a Phase 1 study based on the mTPI design has been published (Fanale, 2011).³⁰

Decision rules are based on calculating unit probability mass (UPM) of 3 dosing intervals corresponding to under, proper, and over dosing in terms of toxicity. Specifically, the underdosing interval is defined as $(0; p_T - e_1)$, the over-dosing interval $(p_T + e_2, 1)$, and the proper-dosing interval $(p_T - e_1, p_T + e_2)$, where e_1 and e_2 are small fractions. Based on the safety profile of PF-06873600 as a single-agent in study (C3661001), e_1 is selected as

0.05 and e_2 is selected as 0.05. Therefore, the target interval for the DLT rate is (0.225, 0.325).

The 3 dosing intervals are associated with 3 different dose-escalation decisions. The underdosing interval corresponds to a dose-escalation (E), overdosing corresponds to a dose de-escalation (D), and proper dosing corresponds to remaining at the current dose (S). Given a dosing interval and a probability distribution, the unit probability mass (UPM) of that dosing interval is defined as the probability of a patient belonging to that dosing interval divided by the length of the dosing interval. The mTPI design calculates the UPMs for the 3 dosing intervals, and the one with the largest UPM informs the corresponding dose-finding decision, which is the dose level to be used for future patients. For example, if the under-dosing interval has the largest UPM, the decision will be to escalate, and the next cohort of patients will be treated at the next higher dose level. Ji et al. (2010)²⁹ have demonstrated that the decision based on UPM is optimal in that it minimizes a posterior expected loss (ie, minimizes the chance of making a wrong dosing decision). The decision rules to “dose escalate” (E), “no change in dose” (S), “dose de escalate” (D) or “dose de escalate, unacceptable toxicity” (U) are described in [Section 3.1.5](#) (see [Table 1](#)).

9.2.2. Statistical Method for Estimating the MTD

This study contains dose escalation and/or de-escalation with single agent in Part 1 followed by a single agent and combination dose expansion (Part 2). The MTD determination will be assessed independently for each dosing regimen evaluated in Part 1A and 1C and dose de-escalation Part 1B based on the mTPI method described in [Section 9.2.1](#). The overall study design is depicted in [Figure 8](#).

Parts 1A and 1C will estimate the MTD/RDE in sequential dose escalation cohorts in:

- HR-positive HER2-negative advanced or mBC patients with prior CDK4/6 inhibitor and endocrine therapy in the advanced or metastatic setting, or
- Locally recurrent/advanced or metastatic TNBC, or
- Advanced platinum resistant epithelial ovarian cancer/fallopian tube cancer/primary peritoneal cancer.

During Part 1 dose finding, all available safety information from safety and biomarker cohorts in Part 1A and 1C will be used to determine the respective MTD/RDE. Because these additional patients in biomarker cohorts will receive a dose lower than the concurrent dose escalation safety cohort or will be enrolled at a dose following the DLT evaluation period in the first 2-4 dose escalation safety cohort patients enrolled, their potential DLT observations may not be strictly used in the mTPI method for the ongoing dose finding in Part 1A and 1C. However, the safety profile from these additional patients in biomarker cohorts will be used to establish the respective MTD or RDE in Part 1A and Part 1C, if applicable.

Part 1B will include PF-06873600 in combination with letrozole and in combination with fulvestrant. The starting dose for this combination will start with PF-06873600 at MTD/RDE for the single agent (established in Part 1A or Part 1C) and the prescribed dose for letrozole and fulvestrant, respectively. The PF-06873600 dose may be decreased if determined to be intolerable in a dose de-escalation manner based on mTPI. The MTD/RDE for this combination regimen, if selected, will be based on 6 to 12 patients.

For data analysis purpose, data from all patients receiving the MTD/RDE in Part 1B and Part 2 expansion cohort will be combined under the same treatment regimen and same tumor type.

Part 2 will evaluate the PF-06873600 dose selected (MTD/RDE) from Part 1 as a single agent (from Part 1A or Part 1C) and in combination with endocrine therapy (from Part 1B).

The dose finding process in Part 1 using mTPI is designed to establish the MTD defined as the highest dose that yields a target of approximately 27.5% probability of DLT and considers equivalent doses that yield probability of DLT in the interval (Equivalence Interval) of (22.5%, 32.5%). The 27.5% target was chosen based on safety considerations and is considered appropriate based on simulations performed on other Pfizer Phase 1 study protocols (ie, B7831001, PF-06671008) and expert input. The prior distribution of DLT is set as a beta (0.5,0.5) and the threshold probability for early termination and dose exclusion is set to 0.95 as suggested in the original mTPI method (Ji et al., 2010).²⁹ A modification of the mTPI could be applied for dose levels that are tested in more than 6 patients: a decision to increase the dose could be made only if the observed DLT rate is <22.5% (2 DLT out of 10 Patients) and a decision to test more patients at a dose only if the DLT rate is below 32.5%. In addition, doses with an incidence of DLT, eg, 4 out of 10, or apparently higher than 32.5% cannot be selected as MTD, even though it might be allowed by the mTPI method.

Cohorts of patients could receive doses already tested but a dose that is associated with decision to “Dose de-escalate, unacceptable toxicity” cannot be revisited and no more patients should be treated at this dose or higher doses for the remainder of the trial.

The maximum sample size for Part 1 would be approximately N=75 for the dose escalation/finding safety cohorts and N=6 to 12 for the biomarker cohorts but actual sample size will depend on the underlying dose toxicity profile and variability in actual data realization.

The study will continue accruing until one of the three stopping conditions below is triggered.

The algorithm will stop if any of the following criteria is met:

1. The maximum sample size has been achieved;
2. MTD has been identified with sufficient accuracy: 6 to 12 patients have been accumulated on a dose that is currently estimated to be the MTD/RDE; or

3. All doses explored appear to be overly toxic and the MTD cannot be determined.

Due to binomial data variability in small samples, DLTs may be observed in a first cohort(s) by chance even when the true Probability (DLT) is fairly low. This could result in the estimated posterior DLT rate to exceed the targeted 27.5% very early in the trial.

The following table shows the probability of escalating to the next dose level for a range of underlying true DLT rates. For example, for a cohort size of $n=3$ and for a DLT that occurs in 10% of patients, there is a greater than 90% probability of escalating. Conversely, for a DLT that occurs with a rate of 70%, the probability of escalating is 3%. It is assumed that dose escalation occurs with either 0/3 or 1/6 patients with DLTs.

Probability of Escalating Dose

True underlying DLT rate	10%	20%	30%	40%	50%	60%	70%	80%	90%
Probability of escalating dose	0.91	0.71	0.49	0.31	0.17	0.08	0.03	0.009	0.001

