
 To document any preliminary evidence of anti-tumor activity of PF-06873600. 	
 Objective Response (OR), as assessed using the Response Evaluation Criteria in Solid Tumors (RECIST) version 1.1. Time-to-event endpoints: eg, Duration of Response (DoR), Progression-Free Survival (PFS), Time to Progression (TTP).

 To evaluate the pharmacodynamic (PD) biomarkers of CDK pathway modulation following treatment with PF-06873600 in tumor. 	
 Modulation of PD biomarkers (eg, pRb, Ki67) of CDK in tumor.

Parts IA and IC: Single Agent Dose Escalation and Part IB: Combination Dose Finding	
CCI [REDACTED]	[REDACTED]
I [REDACTED]	I [REDACTED]
I [REDACTED]	I [REDACTED]
I [REDACTED]	I [REDACTED]

Part 2: PF-06873600 Combination Dose Expansion	
Primary Objective(s):	Primary Endpoint(s):

 To evaluate the preliminary antitumor activity and confirm the safety and tolerability of PF-06873600: 
In combination (at the RDE from Part IB) in patients with:
 
 HR-positive/HER2-negative advanced or mBC (PF-06873600 + fulvestrant) - (second or third line setting). HR-positive/HER2-negative advanced or mBC (PF-06873600 + a nonsteroidal aromatase inhibitor) (CDK4/6i naive). HR-positive HER2-negative advanced or mBC (PF-06873600+fulvestrant) (CDK4/6i naive). 	
 Preliminary antitumor activity measure for efficacy includes ORR, as assessed using RECIST 1.1. Safety and tolerability: 
 Adverse Events as characterized by type, frequency, severity (as graded by National Cancer Institute Common Terminology. Criteria for Adverse Events (NCI CTCAE v 4.03) timing, seriousness and relationship to study therapy. Lab abnormalities as characterized by type, frequency, severity (as graded by NCI CTCAE v 4.03) and timing. Vital sign abnormalities. Heart rate corrected QT interval (eg, QTcF).
Secondary Objective(s):	Secondary Endpoint(s):

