3.1.2. Part 1B PF-06873600 Dose Finding in Combination with Endocrine Therapy

After the single-agent PF-06873600 MTD/RDE has been determined for both the IR and MR formulations, enrollment will be initiated into Part 1B which will evaluate the PF-06873600 in combination with letrozole and in combination with fulvestrant in independent cohorts in women with HR-positive HER2-negative advanced or mBC. PF-06873600 will be administered orally on a continuous basis (unless the dose schedule has changed during Part 1A or Part 1C), while letrozole and fulvestrant will be administered per standard of care. Available safety and clinical data will be reviewed by the safety review team. The PF-06873600 dose in combination with letrozole may be decreased if determined to not be tolerable. The PF-06873600 dose de-escalation in combination with letrozole will follow the mTPI method. Similarly, the PF-06873600 dose in combination with fulvestrant may be decreased if determined to not be tolerable. The PF-06873600 dose de-escalated in combination with fulvestrant will follow the mTPI method. The MTD/RDE of each of the PF-06873600 formulations (IR and MR) in combination with the respective endocrine therapy (letrozole and fulvestrant) will be declared when at least 6 patients have been enrolled at a dose level that is predicted to be the MTD/RDE for each of the respective combination per the mTPI. Once the MTD/RDE of PF-06873600 in combination with letrozole and the MTD/RDE of PF-06873600 in combination with fulvestrant have been confirmed, a recommended dose for expansion for each combination will be declared and enrollment into Part 2 may be initiated. The decision to dose either the MR or IR or MR and IR formulation in Part 2 will be made following a careful review of all available clinical data and in alignment with C3661001 Safety Team.

Similar to Part 1A and/or Part 1C, dose escalation, all safety, PK and PD information from safety cohorts in Part 1B available will be used to determine the PF-06873600 MTD/RDE for the respective combination treatments.

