3.1.7. MTD Definition

The MTD is defined as the highest dose associated with a DLT rate of 27.5% with an equivalence interval of (22.5%, 32.5%) following the mTPI method. During dose escalation/finding, patients will be enrolled in dose cohorts of 1-4 patients in Part 1A and 2-4 patients in Part 1B and Part 1C in dose cohorts other than the MTD/RDE. Each MTD/RDE including single-agent and combination treatments will enroll 6-12 patients. Each patient will receive continuous doses of PF-06873600 every 28 days. The dose finding decision will be based on 1-cycle (28 days) DLT observation period. DLTs observed after the Cycle 1 (28-day) may also be considered in the final determination of the MTD as a single agent, in combination with letrozole, and in combination with fulvestrant.

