4.1. Inclusion Criteria

Patients must meet all of the following inclusion criteria to be eligible for enrollment in the study:

1. Part 1:
 - Patients with HR-positive HER2-negative advanced or metastatic breast cancer (third or fourth line setting) (histologically or cytologically proven).

- Documentation of ER-positive and/or progesterone receptor-positive tumor ($\geq 1\%$ positive stained cells) based on most recent tumor biopsy (unless non-measurable disease where most recent documentation will be provided) utilizing an assay consistent with local standards.
- Documentation of HER2-negative tumor: HER2-negative tumor is determined as immunohistochemistry score 0/1+ or negative by *in situ* hybridization (FISH/CISH/SISH/DISH) defined as a HER2/CEP17 ratio < 2 or for single probe assessment a HER2 copy number < 4 .
- Received one prior line of combined CDK4/6 inhibitor and endocrine therapy.
- Received 1 or 2 prior lines of cytotoxic chemotherapy in the advanced or metastatic setting.
- Measurable disease or non-measurable disease per RECIST 1.1 (with the exception of Part 1B where measurable disease per RECIST 1.1 is required).
- Patients in the biomarker cohort must have a lesion amenable to biopsy.

Part 1A and 1C only:

- **TNBC: Patients with locally recurrent/advanced or metastatic TNBC** who have received up to 2 prior lines of chemotherapy in the advanced or metastatic setting.
 - Documentation of ER-negative and/or progesterone receptor-negative tumor ($< 1\%$ positive stained cells) based on local testing on most recent tumor biopsy (described above).
 - Documentation of HER2-negative tumor based: HER2-negative tumor is determined as immunohistochemistry score 0/1+ or negative *by in situ* hybridization (FISH/CISH/SISH/DISH) defined as a HER2/CEP17 ratio < 2 or for single probe assessment a HER2 copy number < 4 .
- **Ovarian cancer: Patients with advanced platinum resistant epithelial ovarian cancer (EOC)/fallopian tube cancer/primary peritoneal cancer (PPC)** (histologically or cytologically proven) who have received up to 3 prior lines of therapy (NOTE: each line of therapy that includes platinum [as a single agent or in combination] will be considered a unique treatment line).

Part 2:

Arm A:

Patients with HR-positive HER2-negative locally advanced or \geq mBC (second or third line setting) (histologically or cytologically proven).

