- Documentation of ER-positive and/or progesterone receptor-positive tumor (\geq 1% positive stained cells) and HER2-negative tumor (described above).
- Received one prior line of combined CDK4/6 inhibitor and a nonsteroidal aromatase inhibitor with disease progression either on or after treatment.
- More than one prior line of cytotoxic chemotherapy in the advanced or metastatic setting is allowed after discussion with sponsor.
- More than one line of prior endocrine therapy in the advanced setting may be permitted after discussion with the sponsor.
- Have measurable disease per RECIST 1.1. Participants with only non-measurable disease may be enrolled if a compelling clinical rationale is provided by the investigator and approved by the sponsor.

Arm B:

Patients with HR-positive HER2-negative locally advanced or mBC who are naïve to CDK4/6 inhibitors (histologically or cytologically proven).

- Documentation of ER-positive and/or progesterone receptor-positive tumor (\geq 1% positive stained cells) and HER2-negative tumor (described above).
- Have not received a CDK4/6 inhibitor as treatment as adjuvant therapy or as treatment in the advanced or metastatic setting.
- Have not received an aromatase inhibitor in the advanced or metastatic setting (prior adjuvant therapy with AI is permitted).
- One prior line of cytotoxic chemotherapy in the advanced or metastatic setting is allowed if the patient is CDK 4/6 inhibitor naïve.
- Have measurable disease per RECIST 1.1. Participants with only non-measurable disease may be enrolled if a compelling clinical rationale is provided by the investigator and approved by the sponsor.

Arm C:

Patients with HR-positive HER2-negative locally advanced or mBC who are naïve to CDK4/6 inhibitors (histologically or cytologically proven).

- Documentation of ER-positive and/or progesterone receptor-positive tumor ($\geq 1\%$ positive stained cells) and HER2-negative tumor (described above).
 - Have not received a CDK4/6 inhibitor as treatment as adjuvant therapy or as treatment in the advanced or metastatic setting. One prior line of cytotoxic chemotherapy in the advanced or metastatic setting is allowed if the patient is CDK 4/6 inhibitor naïve.
 - Have measurable disease per RECIST 1.1. Participants with only non-measurable disease may be enrolled if a compelling clinical rationale is provided by the investigator and approved by the sponsor.

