2. INTRODUCTION

This document describes the planned statistical analyses for Protocol C3661001 (Amendment 9, to be finalized Mar 2023). This analysis plan is meant to supplement the study protocol. In this document, any text taken directly from the protocol is italicized. Any deviations from this analysis plan will be described in the Clinical Study Report (CSR).

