2.1. Study Design

This is a Phase I/2a, open-label, multi-center, non-randomized, multiple dose, safety, tolerability, pharmacokinetic, and pharmacodynamic study of PF-06873600 administered as a single agent in sequential dose levels and then in combination with endocrine therapy. In Part IA, successive cohorts of patients will receive escalating doses of PF-06873600 starting at 1 mg BID dosed on a continuous basis and then in dose finding (Part IB) with immediate release formulations of PF-06873600 in combination with endocrine therapy (ET) in an outpatient setting. In Part IC, successive cohorts of patients will receive escalating doses of PF-06873600 testing a modified release (MR) formulation in a MR cohort evaluation and then in dose finding (Part IB) with modified release formulations of PF-06873600 in combination with endocrine therapy (ET) in an outpatient setting.

This study contains 2 parts, dose escalation with single agent (Part IA and IC) and then dose finding with PF-06873600 in combination with endocrine therapy (letrozole and fulvestrant, independently with both immediate and modified release formulations) (Part IB) followed by dose expansion arm in combination with endocrine therapy (Part 2). The overall study design is depicted in Figure 1 and Figure 2 below.

The Japan lead-in cohort (J-LIC) will be added separately as a sub-cohort in order to assess the safety of monotherapy of PF-06873600 in Japanese population. Detailed information is provided in the Appendix 7. Japanese participants will be able to enroll into Part 2 after safety and tolerability of monotherapy of PF-06873600 in Japanese participants is confirmed.

In Part IA, Part IB, and Part IC patients will participate in a dose escalation/finding phase aimed at estimating the MTD. The sample size for this component of the study will vary depending on the number of DLTs observed.

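### The Part 2 ORR has no measurable-disease denominator, although Arms A to C may admit patients with only non-measurable disease; as a minor point, the Part 1B and Part 2 pooling sentence needs its scope stated

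*Protocol*

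**What the plan says.** **Measurable disease.** Protocol 4.1, criterion 10, makes measurable disease by RECIST 1.1 an entry requirement for Part 2. The arm-level criteria in the same section ask for measurable disease too. Each of Arms A, B and C then adds an exception: a patient with only non-measurable disease may enter if the investigator gives a rationale and the sponsor approves.

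Protocol Appendix 4 (Table 6) and SAP Appendix 2 (Table 5) give the response categories for patients with non-target disease only: CR, Non-CR/Non-PD, NE and PD. There is no PR. SAP Table 3 estimates confirmed response in two sets. The Full Analysis Set (SAP 6.2) is everyone enrolled. The Response Evaluable Set (SAP 6.5) needs a dose, disease at baseline and one later assessment. Neither refers to measurability.

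**Pooling.** Protocol 9.2.2, on estimating the MTD, states that for data analysis "data from all patients receiving the MTD/RDE in Part 1B and Part 2 expansion cohort will be combined under the same treatment regimen" and the same tumor type. Part 1 patients with HR-positive breast cancer must have "Received one prior line of combined CDK4/6 inhibitor and endocrine therapy". Patients in Arms B and C must "Have not received a CDK4/6 inhibitor as treatment as adjuvant therapy or as treatment in the advanced or metastatic setting". SAP 9.2.2.1 summarizes efficacy for Part 2 and gives listings only for Part 1.

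**The concern.** ORR is reported as an estimate with an exact confidence interval, so its meaning depends on who is in the denominator. A patient with no measurable lesion cannot reach a partial response however much the disease shrinks. Counting that patient lowers ORR for a reason that lies in the response criteria, not in the drug. The two eligibility statements also leave it unclear whether any such patients were enrolled.

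The pooling sentence raises a lesser question. If it were applied to ORR in the letrozole combination, it would place patients who had received a CDK4/6 inhibitor in an arm defined as naive to that class.

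**Working it through.** **Plan's own figures.** Protocol 3.2.1 to 3.2.3 give about 40, 30 and 30 patients in Arms A, B and C. The sum, 40 + 30 + 30 = 100, agrees with the Part 2 total in protocol 9.3.2. The public text shows no benchmark or target response rates, so every ORR below is an assumption.

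**Dilution by non-measurable-only patients.** Let n be the arm size, m the number of patients with only non-measurable disease, p the ORR among the others, and c the CR rate among the m.

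Observed ORR = [p(n − m) + cm] / n = p − (p − c)m/n

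Each such patient therefore costs (p − c)/n, which is p/n if none has a CR. The cost per patient in percentage points, with c = 0, is:

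| Assumed p | n = 30 (Arms B, C) | n = 40 (Arm A) |
|---|---|---|
| 20% | 0.67 | 0.50 |
| 30% | 1.00 | 0.75 |
| 40% | 1.33 | 1.00 |
| 50% | 1.67 | 1.25 |

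- If c = 10% and p = 40%, the cost is (40 − 10)/30 = 1.00 point and (40 − 10)/40 = 0.75 point.
- With p = 40%, n = 30 and c = 0, an m of 1, 2 or 3 gives an observed ORR of 38.7%, 37.3% or 36.0%.
- For scale, the exact 95% interval for 12 responders in 30 is 22.7% to 59.4%.

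**Pooling, for illustration only.** This applies only if protocol 9.2.2 were used for efficacy. Protocol 3.1.7 says "Each MTD/RDE including single-agent and combination treatments will enroll 6-12 patients", so k = 6 to 12 patients could join the 30 in Arm B. The pretreated share is k/(30 + k): 6/36 = 16.7% or 12/42 = 28.6%. The fall in ORR is that share times the assumed gap between naive and pretreated patients. Gaps of 10 to 30 points give 1.7 to 5.0 points for k = 6 and 2.9 to 8.6 points for k = 12.

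Protocol 3.1 plans about 6 IR and about 6 MR patients per endocrine partner, and protocol 3.1.2 treats the formulations separately ("The MTD/RDE of each of the PF-06873600 formulations (IR and MR) in combination with the respective endocrine therapy"). If regimen includes formulation, the share is therefore nearer 17%.

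**The case against.** **On measurable disease.** Entry by exception needs a rationale and sponsor approval, so it should be rare. The SAP already carries a response table for these patients. An ORR over everyone enrolled is conservative, and about one point per patient is small against an interval of 23% to 59%. All of this stands, and it limits the size of the point. It does not remove it: the response table settles how these patients are classified, not whether they belong in the denominator, and the two eligibility statements still conflict.

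**On pooling.** A reader might infer from protocol 9.2.2 that a pooled primary ORR is planned and that nothing rules it out. The documents do not support that.
- The sentence sits in the MTD section, and the efficacy section (protocol 9.4) contains no pooling.
- SAP 9.2.2.1 limits efficacy summaries to Part 2 and only lists Part 1.
- It is tempting to exempt Part 1B from that listing rule, because the rule labels Part 1 as dose escalation while SAP 2.1 describes "dose escalation with single agent (Part IA and IC) and then dose finding with PF-06873600 in combination with endocrine therapy". But the heading of SAP 2.1.4 puts Parts 1A and 1B under dose escalation. SAP 9.2.1 uses the same label for the DLT analysis, and DLT is a primary endpoint in 1A, 1B and 1C.

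A reader might also infer that Arms A and C would be merged because both use fulvestrant. The sentence joins Part 1B to an expansion cohort and does not say that Part 2 arms are joined to each other.

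What remains is that the SAP, which says "This analysis plan is meant to supplement the study protocol", nowhere states that the pooling sentence stops short of efficacy.

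**Conclusion.** The measurable-disease point holds on the text and is the substance of this comment. The primary ORR counts patients who can respond only by CR, and no planned ORR row leaves them out. At an assumed 40% ORR, each one without a CR costs 1.3 points in 30 or 1.0 point in 40. The total effect cannot be computed because their number is not given; it is zero if criterion 10 was applied throughout. A reader might look for a loss of power, but the SAP plans no hypothesis test (4.1, 9.1). The effect is on the estimate and its interpretation.

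The pooling sentence is a minor loose end. Pooled efficacy is not planned; the sentence simply has no endpoint limit and no condition on prior CDK4/6 inhibitor, and it is not expressly reconciled with SAP 9.2.2.1. The 17% to 29% share is conditional on a reading that the SAP does not adopt.

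**What to change.** 1. Add to SAP Table 3 an ORR row for treated patients with measurable disease at baseline, counting those with no post-baseline scan as non-responders. Show it beside the Full Analysis Set ORR, which stays as it is.
2. Report for each arm how many patients with only non-measurable disease were enrolled.
3. Reconcile criterion 10 with the exceptions in the Arm A, B and C criteria.
4. Add one SAP sentence: the pooling in protocol 9.2.2 does not apply to efficacy; ORR, DOR, PFS and TTP are estimated separately for Arms A, B and C from Part 2 patients; and Part 1B efficacy, named as such, is listed.

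The cost is one more row per arm, with a slightly smaller denominator, and one sentence. The baseline lesion data should already be on file. SAP 4.0 is dated 23 March 2023 and primary completion is set for around 5 April 2023, so the SAP changes should be made before the final analysis. The protocol wording can wait for any next amendment.
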